
supplemented with water from the HP system during some weeks in the summer when water use was high. No organic solvent contamination was detected in the drinking water from the other treatment plants serving the base.

1998 ATSDR Study of Adverse Birth Outcomes (“SGA study”)

The Agency for Toxic Substances and Disease Registry (ATSDR) conducted a study of live births to women who resided in base family housing at time of delivery during the period January 1, 1968 through December 31, 1985. Base family housing records were used to identify maternal residence(s) during pregnancy. Information from the birth certificate was used to determine birth weight and gestational age. The study found that “long-term” TCE exposure from HP water was associated with an elevated risk for SGA (OR=3.9, 90% CI: 1.1, 11.9) only among male infants (ATSDR 1998). Exposure to PCE from TT water was associated with elevated risk for SGA among infants born to mothers aged >35 years (adjusted OR=2.1, 90% CI: 0.9, 4.9) and among mothers with two or more prior fetal losses (adjusted OR=2.5, 90% CI: 1.5, 4.3) (Sonnenfeld et al. 2001).

Current ATSDR Epidemiological Study of Specific Birth Defects and Childhood Leukemia

ATSDR is currently conducting a study of birth defects and childhood cancers in children born from 1968 through 1985 to mothers who resided at the base anytime during their pregnancy. Potential cases were identified by a telephone survey of parents conducted by ATSDR during 1999-2002 and were verified using medical records. The phone survey obtained information about the child’s health, the dates of birth of the mother and father, and the dates the parents resided at Camp Lejeune. In 2003, work began on the historical exposure reconstruction of the TT and HP systems.

A total of 106 cases were reported in the survey: 35 NTD, 42 oral clefts, and 29

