Determining the water quality at residences and workplaces at Camp Lejeune is simplified by the fact that, within each water system, the water was completely mixed so all locations served by a water system received similar levels of contamination. It is therefore only necessary to determine in which broad area of the base the residence or workplace is located. The information from the family housing records (for married active duty personnel), the unit identification codes (for single active duty personnel), the MOS code (for active duty workplaces), and the occupation code (for civilian employees), when combined with the information obtained from command chronologies, discussions with knowledgeable former Marines and current base staff, and survey information provided by the respondent, should be sufficient to identify the area of the base where a residence or workplace was located and to determine which water system served that residence or workplace.

Because of uncertainties and variabilities concerning the amount of water each individual routinely consumed (i.e., by ingestion, inhalation and dermal routes), the source of water in the field, the amount of time an individual routinely spent outside the base or in other parts of the base besides the residence, exposure misclassification bias is likely. This bias should be non-differential, i.e., not associated with disease status. However, non-

differential exposure misclassification can distort exposure-response relationships. One approach to reduce the effects of this bias on the exposure-disease relationship is to compare the group with the most certainty of being the highest exposed to the unexposed group. To assess the possible impact of this bias, sensitivity analyses will be conducted assuming different values for the sensitivity and specificity of the exposure classification.

Morbidity Study Population

Persons eligible for the morbidity study are those with accurate and complete addresses who were:

1. Marines and Navy personnel identified from the DMDC computerized personnel database as having been stationed at Camp Lejeune anytime during the period June 1975- December 1985;
2. civilians identified from the DMDC computerized personnel database as having worked at Camp Lejeune anytime during the period December 1972 to December 1985;
3. respondents and their children (who were born prior to 1986 and who are now adults) included in the 1999-2002 ATSDR survey;

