4. Marines stationed at Camp Pendleton anytime during the period June 1975- December 1985, but who were not at Camp Lejeune anytime during the period of drinking water contamination; and
5. civilians employed at Camp Pendleton anytime during the period December 1972-December 1985 who were not at Camp Lejeune anytime during the period of drinking water contamination.

The study population is defined based on available data indicating at which base

the person was stationed or employed. The DMDC personnel records for active duty Marines and Navy personnel do not have information on where the person was stationed (i.e., the unit code) until June 1975. Therefore, the period, June 1975-December 1985 was chosen for inclusion of active duty personnel. The DMDC personnel records for civilian employees began in December 1972 so the period, December 1972-December 1985 was chosen for civilian employees. There is overlap between Marines and Navy personnel included in the DMDC active duty database and the ATSDR 1999-2002 survey; about 65% of the active duty personnel included in the ATSDR survey are also in the DMDC database.

The Camp Lejeune Community Assistance Panel, as well as the panel of epidemiologists convened by ATSDR in 2008, recommended that an unexposed comparison group similar to the Camp Lejeune population be included in order to enhance the scientific credibility of the study. Camp Pendleton was chosen for the comparison population because the base is similar to Camp Lejeune. Camp Pendleton primarily provides training for Marines residing west of the Mississippi while Camp Lejeune primarily provides training for Marines residing east of the Mississippi, although some Marines receive training at both bases. Camp Pendleton has toxic waste sites just like Camp Lejeune. Additionally, the available personnel records are similar for both bases. The major difference is that Camp Pendleton did not have a contaminated drinking water supply.

Current addresses (and if necessary, current names) for the study population will be obtained using a locator firm. The DMDC data includes name, date of birth and social security number. Most of the respondents to the ATSDR 1999-2002 survey provided

their social security numbers, and dates of birth are available for both parents and the study child. Although pregnant women and prisoners are not specifically targeted under this data collection, they will not be excluded.

Sample Size, Power, and Precision of Risk Estimates

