All electronically entered information obtained from surveys will be reviewed for missing data and ambiguous responses. Internal consistency and validity programs will be used to identify and correct coding and data entry errors. The web-based survey will include prompts to alert participants if they incorrectly answer or skip questions; drop down boxes that present ranges of possible answers; and electronic skip patterns that automatically skip irrelevant questions.

Data Analysis

The civilian employees will be analyzed separately from the active duty personnel

and their dependents. This is because the primary exposure to drinking water contaminants for the civilian employees is not the residence, but the workplace location. If the exposure-response relationship for a specific condition in the analysis of civilian employees is observed to be similar to that observed in the analysis of active duty personnel and their dependents, then a combined analysis may be conducted.

In the analysis of active duty personnel and their dependents, there are no dependents from Camp Pendleton. It will be assumed that dependents and active duty personnel with similar residential drinking water exposures (including no exposure) will have similar risks for a condition. In subsequent analyses, effect modification of the exposure-response relationship for a specific condition by whether the respondent was a dependent or active duty personnel will be explored.

Person-time will accumulate from the date the person first resided or worked at Camp Lejeune (or Camp Pendleton) until date of death or the date that the health surveys are mailed. The monthly average levels of contaminants in the drinking water will be used to estimate exposure. The exposure intensity (average and maximum exposure level), exposure duration, and cumulative exposure measures will be calculated. In addition, these exposure measures will be categorized using a priori meaningful cutpoints and/or quantiles based on the exposure distribution of respondents from Camp Lejeune, and cutpoints from a smoothing procedure (e.g., splines or LOESS). The monthly Monte Carlo 95% interval range for each contaminant will be taken into account during the categorization of exposure variables.

The analyses will focus on reported diseases of interest that are confirmed by medical record, death certificate, or cancer registration. However, because medical

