records are generally unavailable for miscarriages, a miscarriage will be considered “confirmed” if affirmative responses are provided to two survey questions: “Did you have a positive pregnancy test before the miscarriage occurred?” and “Was the miscarriage confirmed by a physician or other health provider?” These two questions have been found to improve the accuracy of self-reports of miscarriages (Axelsson 1990).

Poisson regression methods will be used to evaluate exposure-disease relationships, with exposure measures and potential confounding factors included in the models as independent variables. Logistic regression may be used to check the Poisson regression results. Survival analysis methods with age as the time variable may also be used to evaluate relationships between disease and continuous exposure (and confounder) variables. Exposure will be lagged to account for an appropriate latency period for each condition. For most cancers, the initial analyses will lag exposure by 10 years (i.e., a 10-year latency period). Additional analyses will explore other latency periods for each condition. Selection of risk factors for inclusion in the models as confounders will be based on a “10% change in the estimate” rule (Maldonado and Greenland 1993). Models will also be constructed that include well-known risk factors for the disease under evaluation from information obtained in the survey. Ninety percent confidence intervals will be calculated for parameter estimates.

The first confirmed diagnosis of a generalized skin disorder will be used in the analysis. For miscarriage, two approaches will be used. First, we will evaluate only the first pregnancy that occurs at the base. Second, we will include all pregnancies that occur

in the follow-up period and employ the generalized estimating equation (GEE) approach to account for non-independent outcomes arising from multiple pregnancies for the same woman. Induced abortions and ectopic pregnancies will be excluded from the analyses of miscarriage. For the GEE analyses, the logit link will be employed and the correlation structure will assume equal correlation between birth outcomes for the same woman.

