All comparisons will be “internal comparisons” where the Camp Pendleton cohorts will be the unexposed group. If those at Camp Lejeune whose residences were not served by contaminated water have a similar risk for a specific disease as the Camp Pendleton cohorts, then they will be included along with the Camp Pendleton cohorts in the unexposed group. If their risks are observed to be different, then an indicator variable will be included in the analyses that distinguishes the unexposed at Camp Lejeune from the unexposed at Camp Pendleton.

Since drinking water in the field was provided in tanks and “buffaloes” that could have come from anywhere on base, but most likely came from Hadnot Point, it was deemed possible that all active duty personnel were exposed to contaminated drinking water at Camp Lejeune during their field training. This is the primary reason why unexposed comparison groups from Camp Pendleton are necessary. In the subsequent analyses, it will be assumed that all active duty Marines had the potential for drinking water exposures in the field. A variable for field drinking water exposure (based on the contamination levels at Hadnot Point during the period when the individual was stationed at the base) will be added to the Poisson (or Cox) regression models.

Sensitivity Analyses of Selection and Information Biases

For selection bias (or non-response bias) to be present, participation rates must

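### The Lejeune-versus-Pendleton miscarriage contrast is biased downward, because mothers who enter only through the 1999-2002 ATSDR survey were selected on an on-base pregnancy that ended in a birth

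*Protocol*

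**What the plan says.** **Entry.** Item 3 of the eligibility list (Morbidity Study Population) admits "respondents and their children (who were born prior to 1986 and who are now adults) included in the 1999-2002 ATSDR survey". The section on the current ATSDR study of birth defects and childhood leukemia describes that study as covering "children born from 1968 through 1985 to mothers who resided at the base anytime during their pregnancy", and says: "Potential cases were identified by a telephone survey of parents conducted by ATSDR during 1999-2002". A parent's route in through this survey is therefore a birth. There is overlap with the personnel records: "about 65% of the active duty personnel included in the ATSDR survey are also in the DMDC database".

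**Comparison.** Camp Pendleton members are sampled by station or employment. In the Data Analysis section, "the Camp Pendleton cohorts will be the unexposed group", and in the analysis of active duty personnel and dependents "there are no dependents from Camp Pendleton". The section then assumes that "dependents and active duty personnel with similar residential drinking water exposures (including no exposure) will have similar risks for a condition". Effect modification by dependent status is to be explored later. Civilian employees are analysed separately.

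**Miscarriage.** There are two approaches: "First, we will evaluate only the first pregnancy that occurs at the base", and then a GEE over every pregnancy in follow-up. The Study Objectives section describes the sampling frame as unbiased, with no exception for reproductive outcomes.

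**The concern.** A dependent whose only on-base pregnancy miscarried, and who was neither in service nor employed at the base, has no route into the study. A dependent whose only on-base pregnancy ended in a birth does. For ATSDR-only mothers, then, entry depends on the outcome being analysed. The Pendleton women carry no matching condition, so the assumption of similar risk at similar exposure fails for this outcome even if the water had no effect.

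The error runs toward the null or below it. The Protocol's review of PCE calls miscarriage its best-supported reproductive effect, and each exposure-disease pair is to be treated as a separate a priori hypothesis. A real harm could be reported to this community as absent or reversed. Covariate adjustment cannot restore women who never entered the frame.

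**Working it through.** **Inputs.** The Protocol gives no miscarriage risk, no count of on-base pregnancies per woman, and no share of exposed pregnancies from ATSDR-only mothers. Table 1 covers cancers only, so there is no planned figure for this outcome to reproduce. Assumed here: true RR = 1; miscarriage risk p = 0.15 (range 0.10 to 0.20), independent between pregnancies; k = 1, 2 or 3 on-base pregnancies. The Protocol's literature summary gives an average tour of three years, with many shorter, so small k is plausible.

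**Step 1: first on-base pregnancy, given at least one birth among k.**

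P(first miscarried | at least one birth) = p(1 − p^(k−1)) / (1 − p^k)

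| k | Risk at p = 0.15 | Apparent RR at p = 0.10 / 0.15 / 0.20 |
|---|---|---|
| 1 | 0 | 0 / 0 / 0 |
| 2 | 0.15/1.15 = 0.130 | 0.91 / 0.87 / 0.83 |
| 3 | 0.1466/0.9966 = 0.147 | 0.99 / 0.98 / 0.97 |

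Nearly all the bias comes from mothers with a single on-base pregnancy. At three it is close to nil.

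**Step 2: ATSDR-only mothers with one or two on-base pregnancies.** Let s be the fraction of them with one. The risk is (1 − s) × 0.130.
- s = 0.4: 0.078, and 0.078/0.15 = 0.52
- s = 0.8: 0.026, and 0.026/0.15 = 0.17

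**Step 3: a mix that includes k = 3.** Suppose that 50/35/15% of all women with an on-base pregnancy had one, two or three, each woman entering with probability 1 − p^k. At p = 0.15:
- miscarried first pregnancies: 0.35 × 0.1275 + 0.15 × 0.1466 = 0.0666
- women entering: 0.50 × 0.85 + 0.35 × 0.9775 + 0.15 × 0.9966 = 0.9166
- risk 0.0666/0.9166 = 0.0727; apparent RR 0.0727/0.15 = 0.48

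The result barely moves with p (0.49 at 0.10, 0.48 at 0.20). It moves more with the mix: 70/25/5% gives 0.29 and 30/40/30% gives 0.67.

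**Step 4: dilution by women not selected on a birth.** If ATSDR-only mothers supply a share f of exposed first pregnancies, the overall RR is f × 0.4845 + (1 − f).

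| f | 25% | 50% | 75% | 90% |
|---|---|---|---|---|
| Apparent RR (50/35/15% mix) | 0.87 | 0.74 | 0.61 | 0.54 |

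**Step 5: all pregnancies.** Pool the on-base pregnancies of the same ATSDR-only mothers, with each pregnancy counted once:
- miscarriages: 0.35 × 2 × 0.1275 + 0.15 × 3 × 0.1466 = 0.1552
- pregnancies: 0.50 × 0.85 + 0.35 × 2 × 0.9775 + 0.15 × 3 × 0.9966 = 1.5577
- risk 0.0997; apparent RR 0.66, against 0.48 for first pregnancies

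The bias is smaller because women with several pregnancies weigh more, and smaller again if later off-base pregnancies count. It does not vanish, since the qualifying births stay in the denominator. This is a crude pooled rate, not the fitted GEE.

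**Step 6: planned checks.**
- Exploring effect modification by dependent status may expose the problem but corrects nothing.
- The indicator separating unexposed Lejeune from Pendleton leaves Pendleton as the reference for the exposed.
- The selection-bias section works through differential participation. It compares cancers with the mortality study, or asks what would explain elevated rate ratios. An artefact below 1 triggers neither check.

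**The case against.** The exposed group is not made up of birth-selected mothers alone. Lejeune service women come from DMDC regardless of births, and roughly two thirds of the active duty personnel in the ATSDR survey are in DMDC too. The civilian analysis is untouched. All of this stands, and it means the shift scales with an unstated share.

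A reader might infer that exposed rates of miscarriage, infertility and endometriosis are biased downward across the board, or that 0.17 to 0.52 is the study's RR under the null. The documents support neither. That range describes only ATSDR-only mothers with at most two on-base pregnancies. For infertility, DMDC personnel and the survey's adult children are not selected on their own fertility, and a parent of one child can still be diagnosed later. The direction is the same, but the effect is weaker and the Protocol gives nothing to size it. An effect on endometriosis would have to work through infertility; that is inference, and the point is not made here.

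It is also fair that unexposed Lejeune dependents share the birth selection, so the planned comparison of unexposed Lejeune with Pendleton could show the artefact, and an exposed-versus-unexposed contrast within Lejeune could be derived. But that contrast is not the one the Protocol names, and its unexposed Lejeune group would mix selected and unselected women.

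**Conclusion.** The defect is real, in this limited form: in the active-duty-plus-dependents analysis of miscarriage, the contrast with Pendleton is biased downward by the way ATSDR-only mothers enter. The direction follows from the Protocol's own text. The size does not: every figure above rests on an assumed miscarriage risk, number of on-base pregnancies and share of exposed pregnancies. Under those assumptions a null effect could appear as an overall RR anywhere from about 0.87 to 0.54, which is enough to hide a moderate harm. The first-pregnancy analysis is affected most and the all-pregnancies GEE less. Infertility in ATSDR-only parents is pushed the same way by a smaller, unquantified amount. The cancer analyses are not touched by this point. It should be corrected before the miscarriage analysis is run, because neither covariates nor the planned sensitivity analyses will do so.

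**What to change.** - **Miscarriage, dependents:** do not compare ATSDR-only mothers with Pendleton. Compare exposed with unexposed Lejeune dependents, counting only pregnancies conceived after the mother's earliest qualifying study-child birth. The outcomes of those pregnancies cannot have decided her entry.
- **Miscarriage, Pendleton contrast:** limit the Lejeune side to women who are in DMDC in their own right.
- **Infertility:** repeat the analysis without ATSDR-only parents and report both results.
- **Wording:** do not describe the sampling frame as unbiased for these outcomes, and report how many exposed pregnancies come from ATSDR-only mothers.

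This changes the analysis text only; no new data collection is needed. The cost is fewer pregnancies and lower precision for miscarriage. The loss could be substantial among dependents with only one on-base pregnancy, all of whom drop out. It cannot be sized, because the Protocol gives no count of dependents.

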The health survey instrument will collect information on cancers and the following non-cancer diseases of interest: Parkinson's disease, kidney failure and other severe kidney diseases, severe liver diseases, lupus, aplastic anemia, TCE-related skin disorders, scleroderma, multiple sclerosis, motor neuron disease/amyotrophic lateral sclerosis, infertility and endometriosis. In addition, the health survey instrument will include questions on miscarriages occurring to women who were pregnant while residing or working on base. Information about potential confounders will also be collected. Cancers and non-cancer diseases will be confirmed by medical records, death certificates or cancer registrations.

The morbidity study will be conducted to assess whether there is an association between exposure to the contaminated water at Camp Lejeune and specific cancers and the other diseases of interest. Monthly average levels of drinking water contaminants at the residence will be the basis for the primary exposure variables. The monthly average contaminant levels at the Camp Lejeune residences of the study population will be based on the historical reconstruction of the movement of contaminants through the ground

water and into the distribution system. Ground water contamination fate and transport models and water distribution system models will be used to estimate historical monthly averages (and Monte Carlo 95% intervals) of contaminants in the Hadnot Point and Tarawa Terrace drinking water systems during the period when contaminated wells were in use. Because the water in each of these two systems was mixed at the treatment plants prior to distribution, the monthly average contaminant levels in the distribution systems of these systems accurately reflects the contaminant levels in the residences and workplaces served by each of these systems. The residential monthly average contaminant levels will provide the basis for the primary exposure variables: cumulative exposure, average exposure, maximum exposure, and duration of exposure.

To comply with the Congressional mandate, those who registered with the United States Marine Corps (USMC) will also be mailed the same health survey. However, those who were identified solely because they registered with the USMC will not be included in the morbidity study; their self-reported diseases will not be confirmed; and their completed health surveys will be analyzed separately, primarily in a descriptive manner.

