The primary exposure assessment will be based on the contaminant levels in the drinking water serving the person's residence (or workplace location for civilian employees). Each month of residence (or civilian employee's workplace) will be linked to the estimated levels of contaminants in the drinking water serving that location for that month. The person's cumulative exposure will be calculated as well as the average exposure, maximum level of exposure, and exposure duration. These exposure metrics will also be categorized *a priori* into meaningful categories (based on the contaminant level distribution) as well as categorized using a smoothing technique (e.g., LOESS and/or splines). Other possible exposures (i.e., to contaminated drinking water in field training, at the work location of the active duty personnel, or occupational exposures to solvents during the active duty individual's work service) will be explored if sufficient information is obtained from the health survey instrument and personnel databases to assess these exposures.

The military occupation specialty (MOS) code for active duty personnel and the occupation code for civilian employees will be obtained from the DMDC data. Based on discussions with knowledgeable former Marines and current occupational hygiene employees at Camp Lejeune, ATSDR obtained information on the types of chemicals used in various military and civilian occupations at the base. The MOS and civilian occupation codes will be linked to this information to assess potential occupational exposures to chemicals at the workplace.

The locations of workplaces (and the water system serving these locations) will be

based on discussions with knowledgeable former Marines and current staff at Camp Lejeune as well as on survey information provided by the respondent. Drinking water in the field was provided in tanks and “buffaloes”; the water could have come from anywhere on base, but most likely came from Hadnot Point. For this reason, it was deemed possible that all active duty personnel were exposed to contaminated drinking water at Camp Lejeune during their field training and this will be addressed in the data analysis.

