5. The follow-up period for the average participant therefore begins in 1990 (age 29) and continues until 2008 (age 47).
6. Cancer rates for the unexposed are similar to national rates.

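### The repeat-pregnancy miscarriage analysis is not limited to on-base pregnancies and has no pregnancy-specific exposure, so its odds ratio may be diluted or biased in either direction

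*Protocol*

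**What the plan says.** The miscarriage paragraph of Data Analysis sets two approaches, which open as follows: "First, we will evaluate only the first pregnancy that occurs at the base. Second, we will include all pregnancies that occur". For the second approach, the sentence then gives the window and the method: "in the follow-up period and employ the generalized estimating equation (GEE) approach". The GEE model uses a logit link with equal correlation between a woman's pregnancies. The on-base condition is attached to the first approach only, and the follow-up period is not redefined for miscarriage.

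The follow-up defined earlier in Data Analysis is in terms of person-time. Its start is given as "Person-time will accumulate from the date the person first resided or worked at Camp Lejeune", with the same rule for the comparison base. Its end is given separately: it lasts "until date of death or the date that the health surveys are mailed". For cancers, Table 1 assumes that follow-up "continues until 2008 (age 47").

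On what is collected, the opening summary says that the instrument will include "questions on miscarriages occurring to women who were pregnant while residing or working on base". Data Collection lists miscarriages among the conditions asked about and states no on-base limit. The questionnaire itself (Appendix 1) is not shown.

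On exposure, the Exposure Assessment section links each month of residence (or of a civilian's workplace) to that month's contaminant level, and then summarises by person: "The person's cumulative exposure will be calculated as well as the average exposure, maximum level of exposure, and exposure duration". Data Analysis adds that exposure will be lagged by a latency period suited to each condition. No section says how exposure is assigned to a pregnancy that begins after the woman has left the base.

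**The concern.** Three parts of the plan do not fit together: the pregnancies analysed, the miscarriages asked about, and the exposure attached to each pregnancy.

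A pregnancy conceived after the woman left the base, or after the wells closed, has no residential or workplace exposure to this water during gestation. If it enters the model carrying her person-level exposure, it is counted as exposed. If her off-base losses are not collected but the pregnancy is still counted, it enters as a pregnancy without a miscarriage, whatever its outcome.

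This matters because the PCE literature review names miscarriage as the adverse reproductive effect with the strongest evidence, and because the GEE analysis is the only one that uses repeat pregnancies. Neither miscarriage analysis is named as primary. What the questionnaire collects also cannot be corrected once it has been mailed.

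**Working it through.** The protocol gives no risk, odds ratio or sample size for miscarriage, so there is no figure to reproduce. The check is textual first, then illustrative.

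**How wide is the window?** Table 1 assumes that the average participant first came to the base at age 19 in 1980. She or he would be 19 + 5 = 24 at the well closure in 1985 and 47 in 2008, which is 2008 − 1985 = 23 years after closure. This average describes the whole, mostly active-duty cohort. For a woman of that age, much of the childbearing span falls after contamination ended, although few pregnancies would fall near the end of follow-up.

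**Inputs (assumed; none is in the documents).** Baseline miscarriage risk p0 = 0.15. Risk with exposure during gestation p1 = 0.21. Share of a woman's follow-up pregnancies that are on base f = 0.3 to 0.5.

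True OR = (0.21/0.79) / (0.15/0.85) = 0.2658/0.1765 = 1.51.

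**Case A: off-base losses collected, woman-level exposure carried forward, effect confined to on-base pregnancies.** The mixed risk in exposed women is p0 + f(p1 − p0) = 0.15 + 0.06f.

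| f | Mixed risk | Odds | OR against 0.1765 |
|---|---|---|---|
| 0.3 | 0.168 | 0.2019 | 1.14 |
| 0.4 | 0.174 | 0.2107 | 1.19 |
| 0.5 | 0.180 | 0.2195 | 1.24 |

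With a true OR of 2.0 and the same baseline (p1 = 0.261), the pooled OR is 1.72, 1.47 and 1.22 for f = 0.75, 0.50 and 0.25. Baseline risks of 10% or 20% move these by at most 0.02.

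**Case B: all pregnancies counted, only on-base losses recorded.** The apparent risk is f × p, where f may differ between exposed and unexposed women.

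- Equal shares, f = 0.4, true OR 1.51: 0.4 × 0.21 = 0.084 against 0.4 × 0.15 = 0.060. OR = (0.084/0.916) / (0.060/0.940) = 1.44, so there is little dilution. The apparent baseline risk falls from 15% to 6% (4.5% to 7.5% for f = 0.3 to 0.5).
- Unequal shares, true OR 1.0, exposed 0.50 and unexposed 0.33: 0.075 against 0.0495. OR = 0.0811/0.0521 = 1.56.
- Shares reversed: OR = 0.0521/0.0811 = 0.64.

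Unequal shares are plausible by design. Some Camp Lejeune parents enter through the 1999-2002 ATSDR survey, which served a study of children whose mothers lived on base during pregnancy. Camp Pendleton contributes no dependents and has no such route.

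**Case C: only on-base pregnancies are collected and analysed, each with its own exposure.** Then f = 1 and neither distortion arises.

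**The case against.** The strongest reply is that the second analysis may simply mean all on-base pregnancies rather than only the first. If the survey follows the opening summary, off-base pregnancies may never be collected, and Case C applies. The end of follow-up is written for person-time, which a logit GEE model does not use, so survey mailing as the end of the miscarriage window is an inference. Exposure is built from monthly levels, and the text allows a latency period for each condition, so a window suited to miscarriage could be chosen later. Finally, the TCE literature review leaves open whether the oocyte effects seen in animals are transient or permanent, so later pregnancies could carry information.

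Much of this stands. A reader might infer that the odds ratio is certainly diluted, or that the survey certainly asks only about on-base losses. The documents support neither. Dilution of the size in Case A needs off-base losses to be recorded, which is the opposite of on-base-only questions. Data Collection has no on-base limit, and the questionnaire is not shown.

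What does not stand is that nothing needs settling. The benign reading requires adding an on-base condition that the text gives to the first analysis and omits from the second. A lag, as usually applied, discounts recent exposure and keeps older exposure, so by itself it does not confine exposure to gestation. The carry-over question is legitimate, but pooling later pregnancies with on-base ones does not answer it.

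**Conclusion.** The point holds as an inconsistency in the protocol with a conditional effect on the estimate. The GEE population as written is wider than the survey scope given in the opening summary. The only follow-up definition available takes it more than two decades past the well closure, and no rule ties exposure to the pregnancy.

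The effect depends on choices that the documents leave open. Dilution requires that off-base losses are collected, that exposure is held at woman level, and that the effect is confined to exposed pregnancies. Bias in either direction requires that off-base pregnancies are counted without their losses and that on-base shares differ between groups. With equal shares, that second mechanism barely moves the odds ratio. All the magnitudes rest on assumed risks and shares, so they show that the distortion could matter, not how large it will be.

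The first analysis, limited to the first on-base pregnancy, is unaffected. The change is worth making because it is cheap and because part of it must be settled before the questionnaire goes out.

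**What to change.** Reconcile the opening summary, Data Collection and Data Analysis on which pregnancies are asked about, which are analysed, and when the miscarriage window ends.

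- **Population:** define the main GEE analysis as all pregnancies that overlap residence or work at the base, for both Camp Lejeune and Camp Pendleton.
- **Exposure:** assign each pregnancy the modelled monthly levels from around conception to the end of that pregnancy, with no months after it.
- **Later pregnancies:** if off-base pregnancies are collected together with their losses, analyse them separately, coded as unexposed during gestation, as a check for carry-over from earlier exposure. If their losses are not collected, leave them out of the denominator.

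The cost is some rewording and a per-pregnancy link to monthly levels that are already being modelled. The questionnaire must date each pregnancy well enough for that link. The downside is fewer pregnancies in the GEE analysis, and so some loss of precision.
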